5.2 Low Dose Fractionated Radiation Therapy (LDFRT)

All patients will receive 0.5 Gy of radiation therapy twice daily (at least 6 hrs. apart). This study will include a safety run-in component. If > 33% of patients in the initial cohort of 6 experience grade 3 or greater hematologic toxicity (attribution of possible or above) according to the NCI Common Toxicity Criteria version 4, then a dose reduction will occur following the schedule listed below. Otherwise, following a 1 month waiting period after the first cycle of adjuvant LDFRT plus temozolomide for the first cohort of patients, the phase 2 study will open for full accrual. Patients will receive radiation with the first six 28-day cycles of temozolomide.

Safety Run-in Dose Reduction Schedule	
Cohorts	Radiation Schedule
Cohort 1	0.5 Gy bid on days 1-5 of temozolomide
Cohort 2	0.5 Gy bid on days 1-4 of temozolomide
Cohort 3	0.5 Gy bid on days 1-3 of temozolomide
Cohort 4	0.5 Gy bid on days 1 & 2 of temozolomide

6 patients will be enrolled in the initial cohort. Dose reduction will occur if >2 patients experience dose limiting toxicity.

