9.1.2 Endpoints

9.1.2.1 Safety Run-In

9.1.2.1.1 Primary Endpoint

Dose-limiting toxicity (DLT) is defined as hematologic toxicity during the month following cycle #1 of temozolomide plus LDFRT grade ≥ 3 by NCI common toxicity criteria version 4. All patients who receive any amount of LDFRT will be evaluable for toxicity. The recommended phase II dose will be the highest dose yields $\leq 33\%$ DLT rate.

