In the first stage, if 2 or fewer patients of the first 20 accrued to the study show response (PR+CR), the study will be terminated. Otherwise, the study will continue to a second stage with additional 11 patients to a total of 31 patients. If 6 or more out of the 31 patients had PR or CR, the LDFRT plus temozolomide will be considered efficacious and recommended for future comparative study. The estimated probability of early stopping for null is 68%. The probability of early stopping under the alternative hypothesis is 9%. The 6 patients from the selected phase II dose enrolled in the safety run-in will count towards the phase II trial, so that the minimum number of patient for the study is 31 and the maximum is 49.

Safety Monitoring:

Early stopping for toxicity: according to observed severe adverse event (about 5% necrosis rate) that related to RT from the study with higher RT dose than this study among re-radiation HGG patients (Combs JCO 2005), it is very unlikely this low RT dose study will yield DLTs or later RT toxicity as necrosis. However, the study will monitor SAEs (RT related DLTs or Necrosis) continuously through the trial. Assuming the low dose RT related SAE rate follows a binomial distribution. In general, the trial enrollment will be suspend for safety consultation if a posterior probability of SAE rate exceeding 0.2 is great than 60%. The prior for this monitoring rule is a Beta distribution assuming a mean SAE rate of 5%.

September 29, 2022

The safety stopping rule and the operating characteristics are shown below and there are based on 5000 simulations:

SAE event in 2 out of 3 patients. $\Pr(\text{Risk}>0.2 \mid \text{Data}) = 0.6$
SAE event in 3 out of 6 patients. $\Pr(\text{Risk}>0.2 \mid \text{Data}) = 0.7$
SAE event in 4 out of 9 patients. $\Pr(\text{Risk}>0.2 \mid \text{Data}) = 0.76$
SAE event in 4 out of 12 patients. $\Pr(\text{Risk}>0.2 \mid \text{Data}) = 0.62$
SAE event in 5 out of 15 patients. $\Pr(\text{Risk}>0.2 \mid \text{Data}) = 0.69$
SAE event in 6 out of 18 patients. $\Pr(\text{Risk}>0.2 \mid \text{Data}) = 0.74$
SAE event in 6 out of 21 patients. $\Pr(\text{Risk}>0.2 \mid \text{Data}) = 0.63$
SAE event in 7 out of 24 patients. $\Pr(\text{Risk}>0.2 \mid \text{Data}) = 0.69$
SAE event in 8 out of 27 patients. $\Pr(\text{Risk}>0.2 \mid \text{Data}) = 0.74$
SAE event in 8 out of 30 patients. $\Pr(\text{Risk}>0.2 \mid \text{Data}) = 0.65$

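### The run-in's 33% DLT limit and the 20% monitoring limit are not reconciled, and the printed operating characteristics of the monitoring rule do not apply to a trial of 31 patients

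*Combined protocol and SAP*

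**What the plan says.** **Run-in.** Section 5.2 gives the reduction trigger twice. As a percentage: "If > 33% of patients in the initial cohort of 6 experience grade 3 or greater hematologic toxicity", with attribution possible or above. As a count, below the cohort table: "Dose reduction will occur if >2 patients experience dose limiting toxicity". Section 9.1.2.1.1 (safety run-in primary endpoint) states the selection rule: "The recommended phase II dose will be the highest dose yields" a DLT rate of 33% or less. The same section fixes the event and its window: "Dose-limiting toxicity (DLT) is defined as hematologic toxicity during the month following cycle #1 of temozolomide plus LDFRT", at grade 3 or above. Section 2.3 reports that this component is finished and that all patients follow the cohort 1 schedule. It does not give the DLT count.

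**Monitoring.** Under Safety Monitoring, section 9.2.1.2 watches SAEs, specified as RT-related DLTs or necrosis, throughout the trial: "the trial enrollment will be suspend for safety consultation if a posterior probability of SAE rate exceeding 0.2 is great than 60" percent. On the prior: "The prior for this monitoring rule is a Beta distribution assuming a mean SAE rate of 5" percent. That 5% is a necrosis rate from a re-irradiation study at a higher dose. Fourteen boundaries follow, from 2/3 to 13/55, and then a table of operating characteristics. At a true rate of 0.30 the table gives a 99.7% probability of declaring the treatment unsafe, with an average sample size of 24. At a true rate of 0.10 the average sample size is 160.

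**Size.** Section 9.2.1.2 plans 31 patients, with a stated maximum of 49. The six run-in patients on the selected schedule count toward phase II.

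**The concern.** A schedule can meet the run-in limit and then show, in the same patients and those who follow, a rate at which the monitoring rule halts enrollment. A tighter trigger may be what was intended, but the plan never says so. A safety committee asked to consult after a suspension would not know whether a 30% rate of hematologic DLTs is acceptable or a reason to stop.

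The counted event is also unclear, because the plan does not define an RT-related DLT. The prior mean comes from necrosis alone, although the count includes DLTs, and the only DLT definition in the plan is hematologic.

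Finally, anyone relying on the printed 99.7% would overestimate how reliably a trial of this size detects a 30% event rate.

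**Working it through.** **1. Run-in wording.** 2/6 = 33.3%. Read literally, this exceeds 33% (reduce) and is not at most 33% (do not select), but it is not more than 2 patients (do not reduce). The probability of exactly 2 of 6, C(6,2)p²(1−p)⁴, is 0.25 at p = 0.20, 0.32 at 0.30 and 0.31 at 0.40.

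**2. Reproducing the monitoring boundaries.** Only the prior mean, 0.05, is stated. The posterior is Beta(a + x, b + n − x), and the rule acts when Pr(rate > 0.20) > 0.60. Searching over prior weight gives a + b = 6, that is Beta(0.3, 5.7), since 0.05 × 6 = 0.3. This matches all 14 printed values to within 0.005. For example:

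| Events/patients | Observed rate | Printed | Computed |
|---|---|---|---|
| 2/3 | 66.7% | 0.60 | 0.605 |
| 3/6 | 50.0% | 0.70 | 0.696 |
| 4/12 | 33.3% | 0.62 | 0.618 |
| 5/15 | 33.3% | 0.69 | 0.688 |
| 6/18 | 33.3% | 0.74 | 0.744 |
| 8/30 | 26.7% | 0.65 | 0.646 |
| 13/55 | 23.6% | 0.61 | 0.613 |

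**3. Where the rules agree and part.** At 6 patients, 2/6 has posterior 0.41 (no action) and 3/6 has 0.70 (action), the same cut as more than 2 of 6. At 9 patients, 3/9 has posterior 0.53, so an observed one third still does not trigger. From 12 patients it does: 4/12, 5/15 and 6/18 are listed boundaries.

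**4. Size of the divergence.** Assume that every DLT counts as RT related, that each patient has an event with probability p, and that the prior is the one above. Run-in acceptance is P(X ≤ 2) for X ~ Binomial(6, p). Suspension by 31 patients given acceptance comes from exact enumeration of the binomial paths after patient 6. The lower figure uses looks every 3 patients, the upper a look after every patient. The look at 3 patients is ignored.

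| True rate | Accepted at run-in | Suspended by 31, given acceptance |
|---|---|---|
| 0.30 | 0.744 | 0.73–0.78 |
| 1/3 | 0.680 | 0.83–0.87 |

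**5. The printed operating characteristics.** An average sample size of 160 cannot arise in a trial of 31, or of 49. A maximum of about 165 patients, with looks from patient 10 every 5 patients, comes close to the printed table: 3.2, 20.1, 62.4, 99.8 and 100% against 3.3, 18.4, 60.5, 99.7 and 100%, with average sizes 160, 138, 89, 25 and 17 against 160, 140, 91, 24 and 17. At a true rate of 0.30, over all paths from the first patient, the same rule suspends:

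- 81% (looks every 3) to 84% (every patient) with 31 patients
- 91% to 92% with 49 patients

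**The case against.** **The 2/6 conflict is rounding.** If 33% stands for one third, the percentage and count forms coincide and 2/6 is accepted under both. The run-in is also over. This largely stands. A reader might infer that the schedule choice was undefined; the count in section 5.2 gives a workable reading, so that goes too far. What remains is an editorial mismatch and an unreported count.

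**The two rules do not count the same event.** The run-in counts hematologic toxicity in a window around cycle 1, without naming the agent to which it is attributed. Monitoring requires a link to RT, adds necrosis and covers the whole trial. A DLT attributed only to temozolomide might count in the first and not in the second. This stands, and it is why the figures in step 4 are conditional on an assumption. It also shows that the definition is missing.

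**A stricter later trigger is not a contradiction.** One rule leads to a schedule reduction, the other to a pause for consultation, and layered rules are common. This stands too. A reader might infer that a schedule accepted at 2/6 is automatically suspended; it is not, because that posterior is 0.41 and suspension needs further events. The gap is that the plan neither states nor explains the layering.

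**The low prior was deliberate.** Section 9.2.1.2 says that RT-related DLTs, as well as necrosis, are expected to be very unlikely. That is a reason for a low mean, but the only rate it cites is for necrosis.

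**A further inference to avoid.** Section 2.3 reports 5 patients with attributable SAEs and 2 with radionecrosis among 22. A reader might conclude that the rule had already been crossed. Lymphocytopenia plus necrosis gives at most 1 + 2 = 3 of 22 (posterior 0.10). Counting every attributable SAE and necrosis gives 5 to 7 of 22 (posterior 0.41 to 0.76). Neither the overlap nor the countable events are stated, so the documents do not show a crossing.

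**Conclusion.** The concern holds in three parts of unequal weight.

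- **Main part:** a 33% acceptance limit and a 20% monitoring limit stand side by side unexplained, for events that overlap to an undefined degree. The plan's own boundaries suspend at an observed one third from 12 patients on. If the events coincide fully, about three in four schedules with a true 30% rate that pass the run-in are later suspended. If few hematologic DLTs count as RT related, the divergence is smaller; the documents do not allow a figure for that case.
- **Second part:** the printed operating characteristics describe a trial of roughly 165 patients. At a true 30% rate the 99.7% becomes 81%–84% at 31 patients. This rests on the back-solved prior and on the choice of looks, but not on how DLTs are attributed.
- **Minor part:** the 2/6 wording.

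The documents do not support the claim that the same DLT is both accepted and rejected, and nothing here says which limit is clinically right.

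**What to change.** Reconcile sections 5.2, 9.1.2.1.1 and 9.2.1.2:

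1. Write the run-in rule as a single count out of 6, and report the observed run-in DLT count against it.
2. Define which events count as RT-related DLTs for monitoring, including how toxicity possibly due to temozolomide is handled.
3. State how the 33% and 20% limits relate and, if the tighter trigger is intended, say why.
4. State both parameters of the Beta prior, and justify its mean for a count that includes DLTs.
5. Recompute the operating characteristics for 31 to 49 patients with the look schedule that will be used.

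Which limits apply is for the investigators and the safety committee. The cost is protocol wording and a short recalculation. No new data collection is needed.

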The phase 1 component of the study is completed and all patients are being treated according to cohort 1. In general patients have tolerated treatment well with 5 patients with SAEs attributable to the study treatment (fatigue in 2 patients, and lymphocytopenia, aphasia, cognitive disturbance each in 1 patient). Two of 22 patients had pathologically confirmed radionecrosis.

This unanticipated pseudo-progression type response renders our original primary objective of response rate inappropriate. With this amendment we wish to change the primary objective to one year overall survival and enroll the remaining nine patients. The current one year OS is 45.1% (80% CI: 28.2%, 60.9%), the median OS is 9.5 months (median follow-up of 12.7 months) and the median PFS is 4.0 months. Given that patients on this trial have been treated without any severe toxicities, it would be informative to determine if it is possible that there may be a delayed treatment effect that would indicate further study was warranted. Since overall survival is the most definitive endpoint for a clinical trial, we would like to estimate this outcome with the full sample size of 31 and potentially use this information as a reference in a future

clinical trial.

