9.2.1.2 Phase II

Amended Primary Objective: The amended primary objective of the study is one year OS. The current one year OS after 22 patients have been enrolled and followed for a median of 12.7 months is 41.5% (80% CI: 25%, 68%). The one year OS for the historical reference used for this study, TMZ alone (Perry JCO 2010), was reported as 28.6%.

Claiming improvement in one year OS within the context of a protocol with an amended primary objective would not be justified, however, the lower bound of the current 80% confidence interval is fairly promising compared to the historical estimate. Additional follow-up of the current patients and completing enrollment to the sample size of 31 will allow us to estimate one year OS with greater precision: width of current CI 0.33 versus simulated mean width of 0.23, Table 1. A one year OS with a lower bound of an 80% CI greater than 28% would be considered sufficiently promising for further study.

Table 1. Lower bound and mean width of 80% CI for one year OS based on 500 simulations with a sample size of 31

September 29, 2022

Simulated true 12 mo. OS	Simulations with lower bound > 28.6%	Mean width of 80% CI:
0.30	19.8%	0.21
0.35	38.6%	0.22
0.40	59.0%	0.22
0.47	82.8%	0.23
0.50	93.4%	0.23
0.55	98.0%	0.23

Original Primary Objective: The primary objective of this trial is to evaluate the therapeutic efficacy of LDFRT plus temozolomide in patients with recurrent HGG. A true (partial or complete) response rate below 10% is considered clinically insignificant and a true (partial or complete) response rate above 25% clinically is considered clinically significant. A 2-stage design will be used to follow for early termination if there is strong early evidence to support the null hypothesis that the true response rate is at most 10%. The alternative hypothesis is that the true response rate is at least 25%. A total of 31 patients will yield 80% power to detect a response rate (PR+CR) of 25% compared to a 10% rate among patients treated by TMZ alone (Perry JCO 2010) at a one-side alpha level of 0.1. Note that in this study (Perry JCO 2010) the outcomes for the “rechallenge” GBM group was comparable to the AA group.

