SAE event in 9 out of 35 patients. $\Pr(\text{Risk}>0.2 \mid \text{Data}) = 0.64$
SAE event in 10 out of 40 patients. $\Pr(\text{Risk}>0.2 \mid \text{Data}) = 0.63$
SAE event in 11 out of 45 patients. $\Pr(\text{Risk}>0.2 \mid \text{Data}) = 0.62$
SAE event in 13 out of 55 patients. $\Pr(\text{Risk}>0.2 \mid \text{Data}) = 0.61$

Operating characteristics:

Underline true SAE rate	Probability declare unsafe	Average sample size
0.10	3.3	160
0.15	18.4	140
0.20	60.5	91
0.30	99.7	24
0.35	100	17

All SAEs or toxicity events will be tabulated by type and grade based on NCI CTC Version 4.0 for toxicity and adverse events. SAEs with an attribution of possible or above will be evaluated for early stopping. Proportion of individual type of SAE event will be estimated using the binomial distribution along with 95% confidence interval (exact method).

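### The safety rule's operating characteristics belong to a trial of about 160 patients; at 31 patients it detects high SAE rates much less often than printed

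*Combined protocol and SAP*

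**What the plan says.** Section 9.2.1.2 (Safety Monitoring) suspends enrolment for a safety consultation when the posterior probability that the SAE rate exceeds 0.2 is above 60%. The prior is a Beta distribution with mean 5%, whose weight is not given, and monitoring is to be continuous. The section continues: "The safety stopping rule and the operating characteristics are shown below and there are based on 5000 simulations". Fourteen boundary rows follow, every 3 patients from 2/3 to 8/30 and then 9/35, 10/40, 11/45 and 13/55.

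The operating-characteristics table has a column headed "Average sample size". It prints, as probability of declaring unsafe (average size):

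- 10% rate: 3.3% (160)
- 15%: 18.4% (140)
- 20%: 60.5% (91)
- 30%: 99.7% (24)
- 35%: 100% (17)

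The maximum size simulated is not stated.

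On trial size, the same section says "so that the minimum number of patient for the study is 31 and the maximum is 49", and the amended objective speaks of "completing enrollment to the sample size of 31". Section 2.3 reports that "The phase 1 component of the study is completed and all patients are being treated according to cohort 1", with nine patients left to enrol.

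**The concern.** An average sample size cannot exceed the maximum. Three of the five rows exceed both 31 and 49, so the table cannot describe this trial. A rule allowed to run to a much larger size has far more chances to cross its boundary, so the printed probabilities at high SAE rates would be too favourable.

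The table is the plan's only statement of how well this rule protects patients. A safety committee reading it would believe that a 30% SAE rate escapes detection 3 times in 1,000.

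A second point lies in the same section. The counted event is described once as radiotherapy-related DLTs or necrosis, and later as any SAE with at least a possible attribution. These are different sets of patients, and the posterior depends on which one is used.

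**Working it through.** **1. Reproduce the boundary.** With prior Beta(a, b), a/(a+b) = 0.05, and x events in n patients, the posterior is Beta(a+x, b+n−x). Prior Beta(0.3, 5.7), weight 6, returns all 14 printed posteriors to two decimals. For example, 2/3 gives 0.605 (printed 0.6), 8/30 gives 0.646 (0.65) and 13/55 gives 0.613 (0.61). In each row, one event fewer falls below 0.60 (7/30 gives 0.484). The boundary is right.

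**2. Size implied by the table.** In the 10% row, 160 = 0.033·m + 0.967·Nmax, where m is the mean size among stopped trials and lies between 1 and Nmax. So Nmax lies between 160 and (160 − 0.033)/0.967 = 165.4.

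**3. Reproduce the table.** Method: exact forward recursion on the event count, removing at each look the paths at or above the boundary. With a maximum of 164 and looks every 5 patients from patient 4:

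| True rate | Printed: unsafe (mean N) | Maximum 164: unsafe (mean N) |
|---|---|---|
| 10% | 3.3% (160) | 2.7% (160) |
| 15% | 18.4% (140) | 18.7% (140) |
| 20% | 60.5% (91) | 61.2% (91) |
| 30% | 99.7% (24) | 99.7% (25) |
| 35% | 100% (17) | 100% (17) |

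**4. Same rule, maximum 31.** The printed-look column uses only the printed counts, so it needs no assumption about the prior. At patient 31 the boundary is 8 events.

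| True rate | Printed table | Printed looks, last at 30 | Printed looks plus 31 | Every patient to 31 |
|---|---|---|---|---|
| 10% | 3.3% | 6.0% | 6.1% | 7.0% |
| 15% | 18.4% | 18.9% | 19.5% | 21.5% |
| 20% | 60.5% | 39.6% | 41.2% | 43.8% |
| 30% | 99.7% | 80.9% | 82.7% | 84.1% |
| 35% | 100% | 92.0% | 93.2% | 93.8% |
| Mean N, 10% to 35% | 160/140/91/24/17 | 30/27/24/15/12 | 30/27/24/15/12 | 29/27/23/14/11 |

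Simulation agrees. With a look after every patient to 31 (200,000 runs) it gives 43.8% at 20% and 84.1% at 30%.

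**5. Sensitivity at maximum 31.**
- Looks every 5 patients: 34.6% at 20% and 78.7% at 30% (36.4% and 80.8% with a look at 31).
- Looks every 5 from patient 4: 29.8% and 74.5% (33.7% and 79.4% with a look at 31).
- Prior-free ceiling, holding the boundary at the last printed count and looking after every patient from patient 2 to 31: 51.4% and 87.1%.

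Across the schedules tried, the 30% figure runs from 74.5% to 87.1%.

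**6. Larger sizes.** At 49 patients with a look after every patient, detection is 51.3% at 20% and 92.4% at 30%. Reaching the printed figures with a look after every patient takes 88 patients for 60.5% at 20% and 142 for 99.7% at 30%.

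**7. Counted event.** Section 2.3 reports "5 patients with SAEs attributable to the study treatment (fatigue in 2 patients, and lymphocytopenia, aphasia, cognitive disturbance each in 1 patient" and, separately, "Two of 22 patients had pathologically confirmed radionecrosis". Any overlap is not stated. The posterior P(rate > 0.2) at 22 patients is:

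| Events | 2 | 3 | 5 | 6 | 7 |
|---|---|---|---|---|---|
| Posterior | 0.03 | 0.10 | 0.40 | 0.59 | 0.76 |

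Under the narrow description 2 or 3 events are visible: two necroses, plus one lymphocytopenia of unstated grade. Under the broad one there are 5 to 7. Only 7 distinct patients would exceed 0.60.

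**The case against.** The strongest reply is that nothing operational is wrong. The boundary is correct, crossing it only suspends enrolment for consultation, the protocol expects about 5% necrosis, and 22 of 31 patients had already been treated at the amendment. All of this stands, and it limits the point to the rule's stated performance.

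The look schedule also matters. The higher false-alarm figure at 10% comes from look frequency, not trial size: with a look after every patient it is 7.0% at 31 and 7.3% at 164, while looks every 5 patients give 3.2% at 31. Looks every 5 also give 14.1% at a 15% rate, below the printed 18.4%. So what the table gets wrong at 10% and 15% depends on the schedule. The shortfall at 20% and above does not, because sparser looks lower detection further.

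The separate rule in section 9.1.2.1.2, suspension at four symptomatic necroses, adds protection. If every event were such a necrosis, four or more among 31 would occur with probability 89% at a 20% rate and 99% at 30%. That is an upper bound, since the rule ignores hematologic DLTs and other SAEs, and the table does not claim to include it.

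The two event descriptions may be meant as complementary, one naming the event and the other the attribution threshold. The text does not say so.

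**Conclusion.** The point holds. The printed operating characteristics are for a trial about five times the planned size. At 31 patients, under the printed looks or a look after every patient, suspension probability is 40–44% at a 20% SAE rate (printed 60.5%), 81–84% at 30% (printed 99.7%) and 92–94% at 35% (printed 100%). No schedule tried, nor the prior-free ceiling, reaches the printed figures at 20% or 30%.

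The impossibility of the average sizes needs no assumption. The corrected probabilities assume independent events at a constant rate, each known before the next look. With accrual of 1–2 patients per month and late toxicity defined as beyond 3 months, outcomes will lag enrolment, which would delay a suspension.

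The prior weight and the 164-patient schedule are inferred from the printed figures. The printed-look results to patient 30 depend on neither.

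The documents do not show that the boundary was crossed at 22 patients, and section 2.3 alone cannot settle it, since non-serious grade 3 or higher hematologic events are not reported there.

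**What to change.** Replace the table with operating characteristics computed at 31 patients. State beside it the prior parameters, the look schedule, whether there is a look at the last patient, and whether the four-necrosis rule is included. Figures for 49 patients are not needed, because the run-in finished at the first cohort. The row "SAE event in 13 out of 55 patients" and the other rows beyond 31 patients no longer have any effect and can be dropped.

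Reconcile the two descriptions of the counted event, and report the posterior at 22 patients under the reconciled definition.

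The cost is a short calculation and a text correction, with no extra patients and no change to the boundary. The stated detection probabilities will look less favourable and, with the printed looks or a look after every patient, the stated false-alarm chance at a 10% rate rises from 3.3% to 6–7%.
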